4.1.3. Other Efficacy Endpoints

In general, the other efficacy endpoints defined in this section are associated with tertiary efficacy objectives. The other efficacy endpoints are:

7-day point prevalence abstinence is a binary endpoint (success, failure) at each visit from Week 2 through Week 24. At each visit, success will be defined for a subject as having reported smoking abstinence with biochemical verification (CO<10 ppm). 7-day point prevalence for smoking abstinence will be defined as reporting no smoking since the last clinic visit at each weekly clinic visit from Week 2 through Week 12 and over the past 7 days during Follow-up visits at Weeks 16, 20 and 24. Any other outcome will be regarded as a failure. All subjects will have a realization of this endpoint, thereby enabling analyses that follow the ITT principle without imputation.

Serum cotinine levels (ng/mL) are a continuous endpoint measured every other week from Week 2 to Week 12, then at Week 16, Week 20, and Week 24.

Expired CO levels (ppm) are a continuous endpoint measured at each visit from Week 2 through Week 24.

Use of non-cigarette nicotine products, including vaping, will be assessed at each visit from Week 2 to Week 24. Subjects report whether they have used any non-cigarette nicotine products since the last visit (yes, no) and report all products used during the interval (eg, pipe tobacco, e-cigarettes/vaping, marijuana smoking/vaping).

Continuous abstinence from Week 3 to Week 24 (subset analysis): Assess among the subset of subjects who achieve abstinence from Week 3 to Week 6 in Arm A and Arm B (ie, are a

success on the primary efficacy endpoint for primary objective 1). Success will be defined for a subject following the same rules as the continuous abstinence endpoint (see Section 4.1.2.1).

Continuous abstinence from Week 9 to Week 24 (subset analysis): Assess among the subset of subjects who achieve abstinence from Week 9 to Week 12 in Arm A and Arm C (ie, are a success on the primary efficacy endpoint for primary objective 2). Success will be defined for a subject following the same rules as the continuous abstinence endpoint (see Section 4.1.2.1).

Time to failure to maintain abstinence will be evaluated for the subset of subjects who were classified as a success for abstinence at Weeks 3-6. Time to failure to maintain abstinence (days) will be calculated as end date of abstinence minus start date of abstinence +1. The start date of abstinence will be defined as the date of the Week 6 visit. The end date of abstinence will be defined as the earliest date that the subject was known to have resumed smoking, or will be censored, as described below:

- At a visit during the treatment period, if a subject reported smoking since the last visit (either by the subject's self-report or CO ≥ 10 ppm), the end date of abstinence will be the earliest of the following dates: the date the subject reported resuming smoking, or the date of CO ≥ 10 ppm.
- During the follow-up period, if a subject reported smoking a total of more than 5 cigarettes at the attended Week 16, Week 20, and Week 24 visits, or CO ≥ 10 ppm at a visit, the end date of abstinence will be the earliest of the following dates: the date the subject reported smoking the 6th cigarette, or the date of CO ≥ 10 ppm.
- Subjects who have not resumed smoking at their final visit will have end date of abstinence censored at the date of that final visit. (The final visit is expected to be the Week 24 visit.)

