12.2.4. Follow Up Period for Smoking Cessation Assessments

Week 16 (± 1 week)

1. Record the following:
 - a. Has the subject smoked any cigarettes since the last (Day 86/Week 12) clinic visit?
 - b. Has the subject smoked any cigarettes over the past 7 days?
 - c. If subject has smoked, subject should report the total number of cigarettes smoked.
 - d. Has the subject used any non-cigarette nicotine products, including vaping, since the last clinic (Day 86/Week 12) visit? If yes, record what was used and remind subject such products should not be used during the study.
2. Assess for AEs.
3. Blood for cotinine testing.
4. Expired CO.
5. Provide subject with abbreviated behavioral support based on issues/concerns/questions raised ([Appendix 7](#)).
6. All subjects regardless of smoking status are to be scheduled for their Week 20 (± 3 days) follow-up visit.

Week 20 (± 1 week)

1. Record the following:
 - a. Has the subject smoked any cigarettes since the last clinic (Week 16) visit?
 - b. Has the subject smoked any cigarettes over the past 7 days?
 - c. If subject has smoked, subject should report the total number of cigarettes smoked.
 - d. Has the subject used any non-cigarette nicotine products, including vaping, since the last clinic (Week 16) visit? If yes, record what was used and remind subject such products should not be used during the study.
2. Assess for AEs.
3. Blood for cotinine testing.
4. Expired CO.

5. Provide subject with abbreviated behavioral support based on issues/concerns/questions raised ([Appendix 7](#)).
6. All subjects, regardless of their smoking status, should be scheduled for their Week 24 (± 3 days) follow-up visit.

Week 24 (± 1 week)

1. Record the following:
 - a. Has the subject smoked any cigarettes since the last clinic (Week 20) visit?
 - b. Has the subject smoked any cigarettes over the past 7 days?
 - c. If subject has smoked, subject should report the total number of cigarettes smoked.
 - d. Has the subject used any non-cigarette nicotine products, including vaping, since the last clinic (Week 20) visit? If yes, record what was used and remind subject such products should not be used during the study.
2. Assess for AEs.
3. Blood for cotinine testing.
4. Expired CO.
5. Provide subject with abbreviated behavioral support based on issues/concerns/questions raised ([Appendix 7](#)).
6. Discharge subject from study.

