6.3. Definition of Analysis Timepoints

- **Baseline:** The last non-missing observation (including unscheduled visits) prior to the first dose of study drug (cytisinicline and/or placebo), unless otherwise specified. The last non-missing observation prior to the first dose of study drug (cytisinicline and/or placebo), unless for randomized subjects who do not receive study drug then baseline is defined prior to date of randomization. If both a planned assessment and repeat assessment (eg, retest) meet the above criteria and were collected on the same date and time, the repeat assessment will be used as baseline.
- **Change from Baseline:** The change from baseline values will be derived for each subject as the post-baseline value minus the baseline value.
- **End of Treatment (EOT) Visit:** The last clinic visit during the treatment period. Expected to occur at Week 12 (Day 86/EOT visit) for subjects who complete the 12-week treatment period. Subjects who discontinue treatment prior to 12 weeks will have the EOT visit when treatment is discontinued. (See Section 4.2.1.4.)
- **Pre-treatment Period:** Prior to first dose of study drug on Day 1.
- **Treatment Period:** The treatment period is expected to be 84 days (12 weeks) in duration. For an individual subject, the treatment period starts on the date of the first dose of study drug (Day 1), continues through the date of the last dose of study drug, and ends on the date of the Week 12 (Day 86/EOT) visit.
- **Follow-up Period:** The follow-up period is expected to be 12 weeks in duration, and includes the monthly visits at Week 16, Week 20, and Week 24.
- **Study Day:** Study day will be calculated for all assessment dates relative to the first dose of study drug (cytisinicline and/or placebo). The first dose of study drug will be Day 1, and the date preceding Day 1 will be Day –1 which is consistent with the Submission Data Standards (Version 3.1) from Clinical Data Interchange Standards Consortium (CDISC).

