10.2. Analyses of Other Efficacy Endpoints

The other efficacy objectives are stated in Section 3.3. The other efficacy endpoints are defined in Section 4.1.3. Analyses of the other efficacy endpoints will be exploratory. There will be no multiplicity protection scheme for these analyses, and the results of these analyses will be labeled as exploratory.

The results for each endpoint will be displayed graphically by treatment arm. Side-by-side bar charts may be used to display categorical endpoints, Kaplan-Meier figures will be used for time-to-event endpoints. For binary endpoints, forest plots may be used to display 95% CIs for the odds ratio.

For each of the other efficacy endpoints identified below, 3 between arm comparisons will be performed, where appropriate:

- Arm B (cytisinicline 6 weeks) vs Arm A (placebo)
- Arm C (cytisinicline 12 weeks) vs Arm A (placebo)
- Arm C (cytisinicline 12 weeks) vs Arm B (cytisinicline 6 weeks) (this comparison will be two-sided)

The statistical analyses that will be performed for binary endpoints will follow the specification as described for the secondary objectives according to whether the comparison is one-or two-sided. For other than binary endpoints, the analysis methodologies are described below.

10.2.1. 7-day Point Prevalence Abstinence

The 7-day point prevalence abstinence endpoints are binary (success, failure) endpoints defined at each of the following visits: Weeks 2 to Week 12, Week 16, Week 20, and Week 24. The analyses of point prevalence abstinence endpoints will be conducted using all subjects in the All Randomized Set. The analysis methodology for binary endpoints was described in secondary objectives.

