10.2.8. Time to Failure to Maintain Abstinence

Time to failure to maintain abstinence will be evaluated for the subset of subjects who were classified as a success for abstinence from Week 3 to Week 6. Time to failure (days) will be calculated for individual subjects as described in Section 4.1.3. Subjects who are still abstinent at Week 24 will have time to failure censored at the date of the Week 24 visit.

Time to failure will be summarized by treatment arm; the minimum, maximum, median and 95% confidence interval for the median time to failure reported by the LIFETEST procedure will be reported. A Kaplan-Meier figure of treatment arm by time to failure will be produced.

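### The time-to-failure curve loosens its self-report rule at Week 12, which lowers counted relapse there and can favour the 12-week arm by roughly 1 to 5 points if slips cluster soon after stopping drug

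*SAP*

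**What the plan says.** SAP 4.1.3 takes subjects who were abstinent at Weeks 3-6 and starts one clock: "The start date of abstinence will be defined as the date of the Week 6 visit". Failure is then defined in two stretches.

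- **Treatment period.** "At a visit during the treatment period, if a subject reported smoking since the last visit", by self-report or by CO of 10 ppm or more, the subject has failed. SAP 6.3 says that this period "ends on the date of the Week 12 (Day 86/EOT) visit".
- **Follow-up.** Failure by self-report occurs "if a subject reported smoking a total of more than 5 cigarettes at the attended Week 16, Week 20, and Week 24 visits", dated by "the date the subject reported smoking the 6th cigarette" unless a CO of 10 ppm or more comes first.

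Protocol 7.2 gives Arm B cytisinicline for six weeks and then placebo for six, and Arm C cytisinicline for all twelve.

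For the analysis, SAP 10.2.8 specifies medians by arm and states that "A Kaplan-Meier figure of treatment arm by time to failure will be produced". It specifies no test or hazard ratio. The objective (Protocol 6.3 and SAP 3.3, item 9) names B against A and C against A. SAP 10.2 also lists C against B for the other efficacy endpoints, where appropriate. All of these analyses are labelled exploratory.

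**The concern.** A Kaplan-Meier curve is drawn to show when relapse happens. Here the definition of relapse changes part-way along the axis, at the point where Arm C stops drug and visits go from weekly to four-weekly. A reader who sees relapse slow after Week 12 cannot tell behaviour from definition.

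The switch also meets the two active arms at different stages. The strict rule covers Arm B's first six off-drug weeks (6 of its 18 off-drug weeks in this endpoint). It covers none of Arm C's 12, apart from the one to three days between the last dose and the Week 12 visit. The period when each arm first goes without drug is thus judged strictly in one arm and leniently in the other.

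What is at stake is how the B and C curves are read against each other, or how the B-A and C-A contrasts are compared, since both use the same Arm A. There is also a risk of displays that disagree. Secondary objective 3 (SAP 4.1.2.2) lists no Week 7-11 visits, so an Arm B subject who slips at Week 8 but meets the Week 12 and follow-up criteria is relapse-free there and a failure on this curve.

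**Working it through.** The documents give no figure for this endpoint, so there is none to reproduce. The only power figure, 95.7%, belongs to the primary comparisons; full enumeration of Fisher's exact test gives 95.75%, and this point does not touch it.

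**Inputs from the documents.** Clock starts at Week 6; rule switches at Week 12; follow-up ends at Week 24; Arm B is off drug from Week 6 and Arm C from Week 12.

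**Assumed inputs (not in the documents).** Weekly slip hazard l0 = 0.03 in the background, including on drug; l1 = 0.06 to 0.09 in the first six weeks off drug; f = 0.1 to 0.3, the share of follow-up slips that stay at five cigarettes or fewer with CO below 10 ppm.

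**Step at Week 12.** With a constant slip hazard h, the counted hazard is h before Week 12 and h(1 − f) after. For h = 0.05 it drops to 0.045 at f = 0.1 and 0.035 at f = 0.3. Under one constant rule it does not change.

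**Proportion still abstinent at Week 24 under the SAP rule.**

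- Arm B: exp[−6·l1 − 12·l0·(1 − f)]
- Arm C: exp[−6·l0 − 6·l1·(1 − f) − 6·l0·(1 − f)]
- Ratio C/B: exp[6f(l1 − l0)]
- Either arm under one any-cigarette rule: exp[−6·l1 − 12·l0]

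| f | l1 | Arm B | Arm C | C − B, points | Both arms, one rule |
|---|---|---|---|---|---|
| 0.1 | 0.06 | 0.505 | 0.514 | 0.9 | 0.487 |
| 0.1 | 0.09 | 0.421 | 0.437 | 1.5 | 0.407 |
| 0.3 | 0.06 | 0.542 | 0.572 | 3.0 | 0.487 |
| 0.3 | 0.09 | 0.453 | 0.505 | 5.2 | 0.407 |

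For the third row: B = exp(−0.36 − 0.252) = exp(−0.612) = 0.542; C = exp(−0.18 − 0.252 − 0.126) = exp(−0.558) = 0.572.

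When l1 = l0 the ratio is exp(0) = 1 and the gap is zero. If f were 0.5, the gaps would be 5.5 points (l1 = 0.06) and 9.6 points (l1 = 0.09).

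**Simulation check.** With 400,000 subjects per arm, one or two cigarettes per minor slip accumulating towards the limit, l0 = 0.03, l1 = 0.06 and f = 0.5, the SAP rule gave B 0.585 and C 0.640 (formula 0.583 and 0.638). One any-cigarette rule gave 0.484 and 0.487. In the same run, Arm C's counted weekly hazard was 0.030 in Weeks 7-12 and 0.030 in Weeks 13-18 under the SAP rule, against 0.030 and 0.060 under the constant rule. The rule change hid a doubling of slips after drug was stopped.

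**The case against.** The case for leaving the plan alone has five parts.

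1. **The allowance is deliberate.** Protocol 13 applies the Russell Standard in follow-up only, and the sequence of strict and then up to five cigarettes matches secondary objective 1 (SAP 4.1.2.1). This stands. Replacing the rule in the main curve would be a choice, not a correction, and would put its Week 24 level out of line with that endpoint.

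2. **The calendar is the same in all arms.** A reader might infer that Arm C's slips are forgiven and Arm B's are not. The documents do not say that. Arm B's slips in Weeks 12-24, 12 of its 18 off-drug weeks, get the same allowance, and Arm C's are forgiven only up to five cigarettes in total with CO below 10 ppm. The difference is confined to Arm B's Weeks 7-12.

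3. **The between-arm gap depends on early slipping.** This stands: it vanishes when l1 = l0. The premise has some support. Protocol 7.3.2 says relapse after treatment looked high in ORCA-1, and for 3 mg TID abstinence went from 50% at Week 4 to 30% over Weeks 5-8. If the second group is nested in the first, (50 − 30)/50 = 40% were lost within about four weeks. The two measures differ, however, and no ORCA-1 arm stayed on drug to supply a background rate.

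4. **Dating.** A reader might infer that four-weekly visits delay every recorded failure after Week 12. SAP 4.1.3 instead uses the reported date of resuming smoking or of the sixth cigarette; only CO-detected failures are dated at the visit. Still, the visit items in Protocol 12.2.3 and 12.2.4 list yes/no answers and counts, not dates. Whether the CRF captures dates cannot be seen here.

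5. **Status.** The endpoint is exploratory, has no test in SAP 10.2.8, and is not the designated C-against-B comparison, which is secondary objective 3. This stands and limits the point's weight.

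**Conclusion.** The point holds as a limited one about an exploratory display. The self-report rule changes at the Week 12 visit, and for a given slip rate fewer failures are counted afterwards, by the factor 1 − f, in every arm. That follows from the definition whenever f is above zero.

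The advantage to Arm C is conditional: about 1 to 5 points at Week 24 under l0 = 0.03, l1 = 0.06 to 0.09 and f = 0.1 to 0.3, all assumed, and zero without excess slipping soon after stopping drug.

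Two stronger readings go too far. One is that every curve must visibly flatten at Week 12: Arm C's need not, because stopping drug may raise its slip rate just as the rule loosens. The other is a larger gap, which comes from placing every slip in the first six off-drug weeks. The gap is then slip probability times share forgiven, 0.2 × 0.1 = 2 points up to 0.4 × 0.3 = 12 points. The documents give no ground for assuming no slips at other times.

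No primary or secondary inference is affected. This is a cheap improvement, not a defect that must be repaired before the trial can be interpreted.

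**What to change.** In SAP 4.1.3 and 10.2.8:

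- Keep the planned curve with the five-cigarette allowance, and mark the Week 12 rule change on the figure.
- Add a by-arm curve under one rule from Week 6 to Week 24: any reported cigarette since the last visit, or CO of 10 ppm or more. The question is already asked at follow-up visits, for example "Has the subject smoked any cigarettes since the last clinic (Week 16) visit" (Protocol 12.2.4), so no new data are needed.
- State that any reading of C against B, or of timing around Week 12, rests on the constant-rule curve.
- Where the date of resuming smoking is not captured, treat the constant-rule failure as interval-censored between the last abstinent visit and the failing visit, so that the change in visit spacing does not shift that curve. On the planned curve, state how a missing date for the sixth cigarette is handled.

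The cost is SAP wording and one extra analysis. The added curve will show lower absolute abstinence after Week 12 than the planned one, and the text should say why.

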4.2. Safety Endpoints

The safety endpoints are:

- adverse events, including serious adverse events and other significant adverse events
- laboratory assessment
 - hematology
 - chemistry
- vital signs
- 12-lead ECG results
- concomitant medications

4.2.1. Definitions

4.2.1.1. Treatment-emergent Adverse Event

A TEAE is any AE that is new in onset or was aggravated in severity or frequency following the first dose of study drug, up to and including the last visit of the study. Treatment emergence will be determined by comparing the AE start date/time with the actual date/time of first dose of

study drug. TEAEs are defined as events with start date/time on or after the date/time of first dose of study drug. If either the AE start date or start time is unknown on the date of first dose, treatment-emergent events will be defined based on a “Yes” response to the CRF item “Did the AE start after the first dosing?”

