The primary analysis will include all randomized subjects by randomized arm (intent-to-treat analysis). The multiple primary comparisons will be for 6 weeks cytisinicline (Arm B) vs placebo (Arm A) and for 12 weeks cytisinicline (Arm C) vs placebo (Arm A). If the primary efficacy comparison meets statistical criterion, then the corresponding secondary efficacy outcome analyses will have formal meaning. The primary comparisons will be comparing the arms based on the ratio of the odds of success in the experimental arm divided by the odds of success in the control arm (odds ratio) using exact computations for stratified 2x2 frequency tables. The estimated odds ratio and exact confidence interval for the marginal 2x2 table across sites (unadjusted odds ratio), and the estimated difference in proportions and the associated derived exact confidence interval using the exact confidence interval on the odds ratio will also be reported.

Trial Size

The target accrual for each arm is planned for 250 (Approximately 750 for the study). The significance level to be used for the multiple primary comparisons is adjusted from the overall type I error probability of one-sided 0.025 to one-sided 0.0125 using the Bonferroni method to control for multiplicity. The assumed control arm probability of success (Weeks 9-24 abstinence) is 0.07 (7%). The hypothesized experimental arm minus control arm probability difference is specified as 0.12 (12%), corresponding to a hypothesized odds ratio of 3.12 (7% for placebo vs 19% for cytisinicline treatment). The statistical operating characteristics for each comparison are illustrated using simulation with 10,000 replicates. These specifications are consistent with 95.7% power for each comparison with, conditional on 0.07 control arm probability outcome, an odds ratio critical region of ≥ 1.83 , corresponding to a critical difference of ≥ 0.051 (7% for placebo vs 12% for cytisinicline treatment).

Safety

The profiles of adverse events for the arms with regard to incidences of treatment emergent adverse events will be assessed. Treatment emergent adverse events are defined as those events that appear during treatment or are present before treatment and subsequently worsen. Laboratory, vital signs and ECG data will primarily be assessed for clinical safety. Data will be listed and summarized for each treatment according to measurement time.

TABLE OF CONTENTS

SYNOPSIS	2
LIST OF TABLES.....	15
LIST OF FIGURES	15

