14.2.1. Grading Adverse Event Severity

The following grades will be used by an Investigator to describe the severity of all AEs (including clinically-significant laboratory AEs) as shown in [Table 6](#). Only 1 severity grade will be used for each AE (eg, mild - moderate is not acceptable).

Table 6: Adverse Event Severity

Severity of AE	Definition
Mild	No interference with activity
Moderate	Some interference with activity requiring no or minimal medical intervention
Severe	Prevents daily activity and requires medical intervention

If an adverse event has multiple aspects, the aspect in the highest intensity will be graded. It is emphasized that the term severe is a measure of intensity; thus a severe AE is not necessarily serious. For example, itching for several days may be rated as severe; however, may not be clinically serious.

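### SAP 4.2.1.1 counts worsening of a pre-existing AE as treatment-emergent, but its operational rule flags TEAEs by start date alone; unless worsening is recorded as a new AE, such events miss the TEAE summaries

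*SAP*

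**What the plan says.** The concept is stated twice and covers worsening both times. SAP 4.2.1.1 begins: "A TEAE is any AE that is new in onset or was aggravated in severity or frequency following the first dose of study drug". The protocol Synopsis, under Safety, says: "Treatment emergent adverse events are defined as those events that appear during treatment or are present before treatment and subsequently worsen".

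The derivation follows in the same SAP paragraph and uses onset only. "Treatment emergence will be determined by comparing the AE start date/time with the actual date/time of first dose of" study drug, it says, and then: "TEAEs are defined as events with start date/time on or after the date/time of first dose of study drug". If the start date or time is unknown on the day of first dose, the flag rests on a CRF item, "Did the AE start after the first dosing", which is again about onset.

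SAP 11.1 takes its TEAE definition from Section 4.2.1 and starts the AE reporting period at informed consent. Protocol Table 4 schedules AE reporting at both screening visits and on Day 0. Protocol 14.2 lists what is recorded for each AE: description, onset, resolution, severity, relationship, action taken and outcome. That list has no date of worsening and no measure of frequency. Protocol 14.2.1 adds: "Only 1 severity grade will be used for each AE". SAP 13 declares no departures from the analyses planned in the protocol.

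**The concern.** The two definitions in SAP 4.2.1.1 select different sets of events. One includes an AE that "was aggravated in severity or frequency following the first dose of study drug"; the other cannot reach such an AE if its record carries a pre-dose start. The second is the one that can be programmed as it stands. Two programmers working from this paragraph could produce different TEAE flags, one following the concept and the other the start-date sentence.

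The TEAE summaries are the trial's main safety display. As a constructed illustration, suppose mild insomnia is recorded as an AE at screening, becomes severe on Day 10 and leads to a dose reduction. If it stays on one record with a pre-dose start, it is absent from the TEAE tables by severity, by relationship and by dose reduction or discontinuation. Protocol 8.3.1 names insomnia among the AEs that may lead to a reduction. The ORCA-1 safety table (protocol Table 3) was footnoted with the two-part definition, new onset or aggravation, so a start-date-only flag here would not implement the definition stated for that trial.

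**Working it through.** No arithmetic applies. The check is to run the stated rule on each kind of record and compare the result with the stated concept.

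| Record | TEAE by SAP first sentence and protocol Synopsis? | Flagged by the start-date rule? |
|---|---|---|
| (a) Start on or after first dose | Yes | Yes |
| (b) Start before first dose, no worsening | No | No |
| (c) Start before first dose, worsened after dosing, kept on one record | Yes | **No** |
| (d) Start date or time unknown on the day of first dose; began before dosing and worsened afterwards, kept on one record | Yes | **No**: the truthful answer to the CRF item is that it did not start after dosing |
| (e) Start before first dose; worsening entered as a new AE with its own post-dose start | Yes | Yes, through the new record |

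The rule and the concept agree in (a), (b) and (e) and disagree in (c) and (d). Whether a real worsening falls in (c) or (e) depends on how sites record it. Neither the protocol nor the SAP gives an instruction on that.

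Tracing (c) through SAP 11.1, the event is missing from:
- the TEAE rows of the overall summaries;
- the tables by SOC and preferred term, severity and relationship;
- the table of TEAEs leading to dose reduction or discontinuation;
- the after-Week-6 TEAE tables and the summary by time of onset;
- the time-to-first-TEAE figure.

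It remains in:
- the any-reported-AE row of the overall summary, which covers pre-existing events;
- the listing of all AEs and the listing of AEs leading to dose reduction or discontinuation, neither of which is limited to TEAEs;
- the SAE summaries of SAP 11.1.1, if serious.

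The suicidality and depression events of special interest (SAP 4.2.1.3) use C-SSRS and HADS results on or after first dose, so the AE start date does not govern them.

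**The case against.** The strongest reply is that the paragraph is coherent if a worsening is always entered as a new AE, case (e). That instruction would normally sit in the eCRF or the Data Entry Guidelines. SAP 1 says both were reviewed in preparing the SAP, and neither is available here. This stands, and it makes the consequence conditional. It does not remove the mismatch in the text, because the SAP does not say that its start-date rule depends on that practice.

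Three further points also stand.
- The one-grade sentence in protocol 14.2.1 is explained there as barring hybrid grades such as mild-moderate. It does not establish that a worsened AE stays on one record.
- A long-standing complaint may be captured as medical history (protocol 12.2.1). Its worsening on study would then be a new AE with a post-dose start, which the rule flags.
- Protocol 14 puts AEs beginning at randomization in the CRF. Since dosing starts the next day, the pre-dose window on that text is about one day. SAP 11.1 and protocol Table 4 point to collection from screening, so the window itself is unclear.

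A reader might infer that every worsened event certainly drops out of the safety reporting. The documents do not support that: the loss depends on recording practice, and the events stay in the outputs listed above.

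**Conclusion.** The operational TEAE rule is wrong as written. It is narrower than the first sentence of its own section and than the protocol definition, and SAP 13 does not declare the difference. If worsening is not entered as a new record, AEs that "are present before treatment and subsequently worsen" are missing from the TEAE summaries of SAP 11.1. If it is entered that way, the flag works and the plan only fails to say so.

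The size cannot be determined. The documents give no count of AEs present before dosing and no rate of worsening, so any percentage would be pure assumption. A reader might set such a figure against the ORCA-1 rates and conclude that the loss could match the drug signal. Those are single-term rates, while the loss would be pooled over terms, and an active-arm rate is not a difference from placebo. For 3 mg TID against placebo, insomnia was 6.0% against 2.0%, but nausea was 6.0% against 9.8%.

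A reader might also infer that the drug-placebo difference is pulled toward zero. That is not shown. The direction depends on which arm worsens more, and protocol 2.2 says that effects of the drug and of nicotine withdrawal cannot be separated.

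SAP 11 plans no between-arm safety tests, so only descriptive incidence is affected.

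**What to change.** 1. Replace the operational sentence in SAP 4.2.1.1 with: *A TEAE is an AE with start date/time on or after first dose, or an AE with start before first dose whose severity or frequency increased on or after first dose.* For the second kind, use the date of worsening in the after-Week-6, time-of-onset and time-to-first-TEAE outputs, because the original start date would misplace the event there.
2. State in protocol 14.2 and the data entry instructions that a worsening is entered as a new AE record with its own onset date/time and grade. Count each worsening once, because the SAP 11.1 overall summary reports numbers of events as well as subjects.
3. Before unblinding, query sites on AEs with pre-dose onset that were ongoing at first dose, to confirm whether and when they worsened. Do not infer worsening from the action taken alone. No passage shows that the database holds a history of severity changes, so that cannot be assumed as a source.

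Cost: one SAP sentence, one data-entry instruction and a limited query run. TEAE counts may rise slightly.
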